### **3.4.1. Patient compliance monitoring**

The investigator will assess patients' compliance (adherence to the treatment) at the end of the study; the compliance will be assessed by means of the information about administration contained in the diary, completed by the patients for the whole study.

A patient will be declared as compliant with the treatment if he /she has used at least 75 % of the MD, according to Instruction for Use and to standard clinical practice.

### **3.4.2. Concomitant care and interventions that are permitted or prohibited during the study**

Any drug or treatment mentioned in the eligibility criteria as not allowed will be forbidden during the study and its use will have to be avoided by patients, otherwise they are excluded from the participation: use of laser treatment, steroid or non-steroidal anti-inflammatory drugs, analgesics, any anti-hemorrhoidal treatment (both drugs and dietary supplements), anticoagulants, and antiplatelet agents will be not allowed during the whole study.

No restriction on treatments taken previously by patients for medical conditions not related to this study protocol will be envisaged.

Patients will be advised to note any concomitant treatment or medications or any major modification to their diet and / or lifestyle in the diary.

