Procedures	
Visit 1 Screening / Baseline visit (day 0)
 
 
• Informed consent / Eligibility Criteria
 
• Demographics / Medical History / Physical examination and vital signs (including haemorrhoids evaluation and confirmation of diagnosis)
 
• Concomitant treatments and medications assessment
 
• Quality of life assessment by means of the Short Health Scale for Haemorrhoidal Disease (SHSHD) by patient
 
• Haemorrhoid Severity Score (HSS) by Investigator
 
• Haemorrhoidal Disease Symptom Score (HDSS) by patient
 
• Diary supply
 
• MD supply
 
 
Visit 2 End of Study visit (day 14 <math>\pm</math> 2 days)
 
 
• Treatment adherence
 
• Diary's maintenance
 
• Physical examination and vital signs (including haemorrhoids evaluation)
 
• Concomitant treatments and medications assessment
 
• Quality of life assessment by means of the Short Health Scale for Haemorrhoidal Disease (SHSHD) by patient
 
• Haemorrhoid Severity Score (HSS) by Investigator
 
• Haemorrhoidal Disease Symptom Score (HDSS) by patient
 
• Diary collection
 
• MD collection
 
• Safety assessment by AE / ADE / DD collection
 
 
Phone call (day 30 <math>\pm</math> 1 day)
 
 
• Treatment adherence
 
• Diary's maintenance
 
• Safety assessment by AE / ADE / DD collection
 

Not allowed concomitant treatment or	Any drug or treatment mentioned in the eligibility criteria as not allowed will be forbidden during the study and its use will have to be avoided by patients, otherwise they are excluded from the participation: use of laser treatment,

medications	
steroidal or non-steroidal anti-inflammatory drugs, analgesics, any anti-haemorrhoidal treatment (both drugs and dietary supplements), anticoagulants, and antiplatelet agents will be not allowed during the whole study.
 
No restriction on treatments taken previously by patients for medical conditions not related to this study protocol will be envisaged.
 
Patients will be advised to note any concomitant treatment or medications or any major modification to their diet and / or lifestyle in the diary.

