Statistical analysis	
Statistical analyses will be conducted on all patients who have successfully completed the study without a protocol deviation that is regarded as impacting the assessment of the key variables (as per protocol). The quality and completeness of the collected data will be evaluated preliminarily compared to data analysis. If a patient is missing information for one or more variables, even after the resolution of its query, the missing data will not be replaced. If a patient has been involved in violation of inclusion/exclusion criteria, the respective data will be excluded from the analysis. Quantitative variables (i.e., demographic) if normally distributed will be described through media, and standard deviation (SD); non-normally distributed variables will be described using median and range of interquartile. The Student's t-test and the Mann-Whitney U will be employed to perform comparative analysis in accordance with the distribution of these variables. Factorial variance analysis can also be used to evaluate any interactions between quantitative variables and linear progression models to relate possible confounding bias with independent variables. Categorical variables will be finally described using frequencies and percentages and comparative analysis will use the <math>\chi^2</math> test.
 
The overall type I error rate will be preserved at 5%. All tests will be two-sided. Data from unscheduled visits will not be included in the analysis.

GCP Statement, Guidelines and legislation	
The protocol is developed in accordance with the following:
 
 
● International Standard ISO 14155:2020 (10).
 
● Regulation (EU) 2017/745 of the European Parliament and of the Council of 5 April 2017 on medical devices (11).
 
● ICH 6 Harmonized Tripartite guidelines for Good Clinical Practice (ICH GCP) requirements (12).
 
● Local legislation.
 

Timing	Submission to Competent Authority	January, 2024
	Approval by Competent Authority/EC	February, 2024
	Start of enrolment (FPI)	February, 2024
	End of enrolment (LPI)	September, 2024
	End of treatment (LPO)	October, 2024
	Final Report of trial	December, 2024

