#### Visit 2 (day 14 $\pm$ 2 days)

During this visit, the Investigator will perform the following examinations and the e-CRF will be completed accordingly:

- Physical examination (according to what was already performed at visit 1: pulse, blood pressure, weight / height and BMI will be evaluated), including haemorrhoidal disease evaluation.
- Concomitant treatments and medications assessment.
- Evaluation of compliance (MD administration assessment by means of the patient's diary carried out by Investigator).
- Diary and MD (used, partially used, or unused containers) collection.
- Safety assessment by AE/ADE/DD collection.

During this visit the following questionnaires will have to be completed:

- HR-QoL questionnaire: SHSHD (by patient)
- HSS (by Investigator)
- HDSS (by patient)

Patients who discontinued the protocol, will be visited reporting on the last visit page all the safety assessments and (if possible) the examinations and questionnaires requested for the last visit.

Patients who discontinued the protocol, will be visited reporting on the last visit page all the safety assessments and (if possible) the questionnaires requested for the last visit.

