#### **4.3.2. Statistical design, method, and analytical procedures**

Design: Open, non-comparative, multicentre, prospective, interventional trial.

The principle of intention-to-treat (ITT), as far as practically possible, will be the main strategy of the analysis adopted for the primary endpoint and all the secondary endpoints. These analyses will be conducted on all participants.

No imputations will be made on missing data.

The statistical plan details the following 3 analysis sets which will be evaluated in this study:

- The ITT population, which includes each patient enrolled in the study that used at least one dose of the investigational product and had at least one efficacy assessment.
- The Per-Protocol population, which excludes patients with major protocol deviations or violations (e.g., did not use the investigational product, did not attend all the visits, or had missing data regarding the primary endpoint) and includes those with valid observations on the primary endpoint.
- Safety population, which includes each patient enrolled in the study that used at least one dose of the investigational product.

The protocol outlines that a two-sided p-value of 0.05 or less will be used to declare statistical significance for all analyses. Similarly, all confidence intervals will be calculated at the 95% level.

No adjustment for multiplicity will be made to adjust the type 1 error rate for secondary endpoints. If necessary, relevant results from other studies already reported in the literature will be considered in the interpretation of results.

If a patient is missing information for one or more variables, the missing data will not be replaced.

All statistical analyses will be performed using the R statistical software v 4.2.2 (9), or the latest stable version at the time of statistical analysis.

The final analysis will be completed after all patients have been exited from the study, all queries have been resolved, and the database has been locked.

The overall type I error rate will be preserved at 5%. All tests will be two-sided. Data from unscheduled visits will not be included in the analysis.

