Statistical analyses will be conducted on all patients who have successfully completed the study without a protocol deviation that is regarded as impacting the assessment of the key variables (as per protocol). The quality and completeness of the collected data will be evaluated preliminarily compared to data analysis. If a patient is missing information for one or more variables, even after the resolution of its query, the missing data will not be replaced. If a patient has been involved in violation of inclusion/exclusion criteria, the respective data will be excluded from the analysis. Quantitative variables (i.e., demographic) if normally distributed will be described through mean, and standard deviation (SD); non-normally distributed variables will be described using median and range of interquartile. The Student's t-test and the Mann-Whitney U will be employed to perform comparative analysis in accordance with the distribution of these variables. Factorial variance analysis can also be used to evaluate any interactions between quantitative variables and linear progression models to relate possible confounding bias with independent variables.

Categorical variables will be finally described using frequencies and percentages and comparative analysis will use the  $\chi^2$  test.

The safety analysis will be done on the safety population.

Minor deviations from the original statistical plan (SAP) will be considered acceptable (e.g., due to the non-parametrical form of the data, statistical tests will be adjusted accordingly). Major deviations from the SAP will be reported by the statistician to the Clinical Project Manager and will result in clinical trial protocol amendments.

Tables will include baseline characteristics of the participants, medical history and concomitant medications, and safety outcomes. A CONSORT diagram illustrating the flow of patients through the study is also planned.

Additional details about statistical analysis will be documented in the Statistical Analysis Plan (SAP), enclosed in the Trial Master File.

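### Excluding users of prohibited treatments and analysing completers only can remove patients who lacked relief; no such loss is shown, but use among the 50 is unreported

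*Combined protocol and SAP*

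**What the plan says.** Protocol section 3.4.2 lists treatments that may not be used during the study: laser, steroids, NSAIDs, analgesics, any anti-haemorrhoidal drug or supplement, anticoagulants and antiplatelets. On use of any of them it says that "its use will have to be avoided by patients, otherwise they are excluded from the participation". The synopsis repeats this: "otherwise they are excluded from the participation: use of laser treatment".

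The analysis text points two ways.

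- Section 4.3.2 says that intention-to-treat, as far as practicable, "will be the main strategy of the analysis adopted for the primary endpoint and all the secondary endpoints". It defines separate ITT, per-protocol and safety sets.
- The synopsis says "Statistical analyses will be conducted on all patients who have successfully completed the study without a protocol deviation" that is judged to affect the key variables. Section 4.3.2 repeats the sentence and adds: "If a patient has been involved in violation of inclusion/exclusion criteria, the respective data will be excluded from the analysis".

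On missing scores, section 4.3.2 says "No imputations will be made on missing data". Under Visit 2 in section 3.7.2.1, discontinued patients are seen again for safety assessments and "if possible) the examinations and questionnaires requested for the last visit".

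On reporting, section 4.3.2 says "Tables will include baseline characteristics of the participants, medical history and concomitant medications, and safety outcomes", and plans a CONSORT flow diagram. The patient diary asks for the name of every drug taken, and the CRF has a concomitant-medication field at each visit. CRF section 8 records the reason for leaving, and protocol section 5 requires deviations to be recorded.

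**The concern.** The patient with most reason to take a painkiller or another haemorrhoid product is the one whose symptoms persist. If use ends participation, and only completers are analysed, the chance of being dropped depends on the outcome. With no control arm, the primary result is simply the mean change in those analysed, so losing poor responders raises it.

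Intention-to-treat as the main strategy does not close the gap by itself. A removed patient may have no Visit 2 score. Without imputation that patient has no change score and cannot enter the paired test, even if nominally in the ITT set.

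For this completed trial there is a second, narrower issue. If any of the 50 took another treatment and stayed in, the report credits their whole fall to the device, and the reader cannot tell whether this happened.

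**Working it through.** **1. The reported result.** From Table 5, 14.04 − 7.80 = 6.24 with SD 5.51. The standard error is 5.51/√50 = 0.779, so t = 6.24/0.779 = 8.01 (Table 5.1 prints 8.003921). The 95% CI is 6.24 ± 2.01 × 0.779 = 4.67 to 7.81, as printed.

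**2. Was anyone lost?** Section 9 (Demographic Dataset) reports 50 enrolled, Table 4 has N = 50, and Table 5.3 has 34 + 16 = 50. The signed-rank statistic gives the same count. With no negative change (minimum 0 in Table 5), the statistic equals n(n+1)/4 for n non-zero changes, and 46 × 47/4 = 540.5, the printed value. So 46 improved, 4 were unchanged, and 46 + 4 = 50.

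**3. Is use reported?** The contents list, the index of tables and the results summary show no concomitant-medication table and no count of listed treatments. The four indexed figures are the age distribution and the plots for the three scales, so none is the flow diagram.

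**4. Users among the 50, change set to zero.** The number of users, k, is an assumption; no document gives a rate. The falls sum to 50 × 6.24 = 312. The new mean is (312 − sum of the users' falls)/50.

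| Assumed users | Least improved | Average | Each fell by 18 |
|---|---|---|---|
| 1 | 312/50 = 6.24 | (312 − 6.24)/50 = 6.12 | (312 − 18)/50 = 5.88 |
| 5 | 311/50 = 6.22 | (312 − 31.2)/50 = 5.62 | (312 − 90)/50 = 4.44 |

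The 6.22 takes the four unchanged patients and one with a fall of 1. Table 5 has a first quartile of 2, so the fifth-smallest fall was 1 or 2; at 2 the figure is 310/50 = 6.20. An integer search using the Table 5 summaries, the sum of 312 and the sum of squares (49 × 5.5127² + 50 × 6.24² = 3436) allows up to seven falls of 18. The last column is therefore possible, but nothing shows that it occurred.

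**5. Patients removed and not counted.** This is the quantity that speaks to loss through exclusion. Adding k patients with zero change gives 312/(50 + k): 6.12 for one and 312/55 = 5.67 for five.

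**6. The test.** Setting five of the 50 to zero leaves at least 41 non-zero changes, all positive, so the exact two-sided p is at most 2 × 0.5⁴¹ = 9.1 × 10⁻¹³. Suppose instead that uncounted excluded patients had worsened and held the largest ranks. Then T⁺ = 46 × 47/2 = 1081, with n = 46 + k, mean n(n+1)/4 and variance n(n+1)(2n+1)/24. By the normal approximation p = 0.00009 for k = 5, 0.043 for 11 and 0.081 for 12. Every mean above also exceeds the planned fall of 7.90 − 6.20 = 1.70 (section 4.3.1).

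**The case against.** The strongest reply is that the harm did not occur on the record. Barring confounding treatments is ordinary in an uncontrolled trial. Use is recorded, a final visit is offered, reasons for leaving are kept, and all 50 are in the tables. What remains for this trial is a reporting gap. That much stands, and it limits the point.

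Three further objections also stand.

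- A reader might take 4.44 as the likely true fall. If users were the patients without relief, as the mechanism supposes, the mean barely moves (6.22). The 4.44 needs five users who were all maximum responders.
- A reader might treat use during the study as an eligibility violation, because section 3.4.2 borrows its list from the eligibility criteria. That is strained: section 3.3.4 settles eligibility before enrolment. The completers-only sentence is what clearly removes an excluded patient.
- A reader might count every analgesic or NSAID entry as device failure. Section 3.3.1 limits the washout to treatments for haemorrhoids, and section 3.4.2 places no restriction on earlier treatments for unrelated conditions. Some use may therefore be permitted.

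The objections do not remove the flaw in the text. The recording rules do not preserve a score, exit questionnaires are optional in practice, and section 4.3.2 contradicts itself on who is analysed.

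**Conclusion.** The point holds as a defect in the written rule and a gap in the report, and the sponsor should act on both. Followed as written, sections 3.4.2 and 4.3.2 can drop patients because they lacked relief.

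A reader might infer hidden removals from zero loss against the planned 10% drop-out: if 10% were the true rate, the chance of no loss in 50 is 0.9⁵⁰ = 0.005. But that 10% is a planning allowance, not an observed rate, and the documents show no removed patient. Nor do they support doubt about significance: at least 12 uncounted patients, all with the worst ranks, would be needed.

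Only the size of the fall is open. On the assumed range of one to five users among the 50, the mean lies between 4.44 and 6.24, against the reported 6.24. Five uncounted excluded patients with zero change would give 5.67. If nobody used a listed treatment and nobody was removed, the reported figures stand. The separate SAP in the Trial Master File was not among the documents; it might settle the ITT conflict, but as a plan it would not supply a count of use.

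**What to change.** **For this trial.** Report from the diaries and CRFs how many of the 50 used a listed treatment before Visit 2, with the reason where recorded. Supply the planned concomitant-medication table and flow diagram. If use for haemorrhoid symptoms is found, show beside the primary result a sensitivity analysis with those patients' change set to zero. List use with no recorded reason separately, and do not count it as failure by default.

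**For the protocol text, if it is used again.**

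- In section 3.4.2 and the synopsis, replace exclusion from participation with recording of use (date and reason) and completion of SHS-HD, HDSS and HSS at Visit 2.
- In section 4.3.2 and the synopsis, make ITT with observed scores primary, whatever treatment was used.
- Limit the completers-only and eligibility-violation sentences to the per-protocol set already defined.

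Which treatments are barred remains for the sponsor and investigator.

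**Cost.** Low: a count from records already held, one table, one diagram and at most one rerun of the primary test; for the protocol, a few sentences and a reason-for-use field. Visit 2 is already scheduled. The price is that observed scores may include the effect of the other treatment, and zero change is a convention.

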### **3.5. STUDY PROCEDURES AND COLLECTED VARIABLES**

#### **3.5.1. Outcomes**

The following outcomes will be evaluated:

##### Primary outcome

- The Short Health Scale for Haemorrhoidal Disease (SHSHD) (Annex 3 “Collected variables”) (5,16,17) will be used to evaluate the QoL. The questionnaire will be administered by the Investigator to each patient during the study visit, at baseline and on day 30, in PAPI mode (Paper and Pen Interview) (15).

The Short Health Scale (SHS) is a patient-reported measurement instrument of subjective health originally developed for patients with inflammatory bowel disease (IBD) (16–18). SHS was proposed as a simplified HRQoL (Health-Related Quality of life) instrument with just 1 question in each of its 4 dimensions, including symptom burden, functional status, disease-specific worries, and general well-being. SHS was adapted for HD (Short Health Scale for Haemorrhoidal Disease - SHSHD) in accordance with the Consensus-Based Standards for the Selection of Health Measurement Instruments (COSMIN) guidelines; SHSHD has shown to be a reliable and responsive measure for HRQoL. Patients are asked to report overall symptom load, interference with daily activities, and worries caused by HD. The fourth question regarded general well-being. A 7-point Likert scale, giving a total score ranging from 4 to 28 is used.

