Objectives	This trial aims to evaluate the overall performance and safety of the MD PROCTOeze® PLUS in relieving symptomatology of haemorrhoidal disease and

	
anal irritation in adult patients affected by Grade I-II (Goligher classification) haemorrhoids as assessed by the patient and the Investigator at the end of the treatment period.
 
The primary objective is the assessment of performance by the improvement in the quality of life (QoL).
 
Secondary objectives are the assessment of performance by validated scales completed by the Investigator and by the patient at the end of the treatment period.
 
The safety of the MD will be evaluated through Adverse Events (AE) and Adverse Device Effect (ADE) incidence assessed by Investigators and reported according to the current legislation.

Outcomes	
Primary outcome
 
 
• The Short Health Scale for Haemorrhoidal Disease (SHSHD) (5) will be used to evaluate the QoL. The questionnaire will be completed by the patient at baseline and day 30, at the end of the treatment with the MD.
 
 
Secondary outcomes
 
 
• The Haemorrhoid Severity Score (HSS) (6), a physician-reported outcome, will be completed by Investigator at baseline and day 30, at the end of the treatment with the MD.
 
• The Haemorrhoidal Disease Symptom Score (HDSS) (5), a patient-reported outcome questionnaire, will be administered by Investigator to each patient at baseline and at day 30, at the end of the treatment with the MD.
 
• Evaluation of AE, SAE, ADE, SADE, ASADE, USADE incidence assessed by Investigator and reported according to the current legislation for the whole study period. DD will be also evaluated.
 

Design	Open, non-comparative, prospective, interventional trial.
Disease	Hemoroidal disease :Grade I – II symptomatic haemorrhoids (according to Goligher classification)
Population	Adult patients affected by Grade I-II (Goligher classification) haemorrhoids that did not need hospitalization and treated as outpatients (the treatment will be self-administered at home).

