## **2.2. RESEARCH HYPOTHESIS**

The Research Question of the present trial is the following: in a population of adult patients, men and women, suffering from symptomatic haemorrhoids, will the administration for 4 weeks of the IMD PROCTOeze® PLUS improve the haemorrhoidal symptomatology, giving results assessed at the end of the treatment by means of validated questionnaires?

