##### Secondary outcomes

- The Haemorrhoid Severity Score (HSS) (Annex 3 “Collected variables”) (6), a physician-reported outcome, will be completed by Investigator at baseline and day 30, at the end of the treatment with the MD.

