##### safety outcome

- Evaluation of AE, SAE, ADE, SADE, ASADE, USADE incidence assessed by Investigator and reported according to the current legislation for the whole study period. Device Deficiencies (DD) will be also evaluated.

The HS is a physician-reported measurement instrument based on PNR-Bleed classification, that classifies and describes the haemorrhoids based on the four main characteristics of the hemorrhoidal disease i.e., the degree of hemorrhoidal Prolapse (P), Number (N) of the primary hemorrhoidal columns involved, Relation (R) of the haemorrhoidal tissue to the dentate line and the amount of Bleeding (B) from it. All four components in this classification system are graded into five grades ranging from 1 to 5. Grade 1 is the normal anal cushions and Grade 5 is the worst grade in a specific characteristic. HSS is the total score obtained by the sum of the numerical grades of all four characteristics of haemorrhoids in the PNR-Bleed classification. The minimum HSS score is 4 and the maximum score can be 20. The HSS score of a normal person without any signs and symptoms of haemorrhoids is 4. Calculation of the HSS help in the quantification of the haemorrhoidal disease for further reference and is helpful in post-treatment patient follow-up to grade the response to treatment and to assess the effectiveness or failure of any particular treatment regimen for haemorrhoids. It may also be used in predicting and diagnosing the recurrence after any form of treatment for the haemorrhoids.

- The Haemorrhoidal Disease Symptom Score (HDSS) (Annex 3 “Collected variables”) (5,19) is a patient-reported outcome. The questionnaire will be administered by Investigator to each patient at baseline and on day 30, at the end of the treatment with the MD.

The HDSS is a patient-reported measurement instrument. It comprises five items. Symptoms are assessed using the patient-reported frequency of the 5 symptoms, including pain, itching, bleeding, soiling, and prolapse. Patients are instructed to answer based on their experience during the previous period. Each symptom is graded on a 5-point scale (0 = never, 1 = less than once a month, 2 = less than once a week, 3 = 1–6 days per week, 4 = every day or always), giving a total score ranging from 0 to 20.

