The importance of duly completing the diary will be stressed by the Investigator. The completed diary will be collected at the end of the study (at V2). Patients will be advised to note any major modification to their diet

and / or lifestyle in the diary. Moreover, patients will be informed (it will be written in the diary) that they will receive a phone call from the investigator 30 days after the end of the study to check if there have been AEs. The following visit (V2) will be scheduled 14 ( $\pm$  2) days after V1; a phone call will be scheduled 30( $\pm$  1) days after V1.

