### **4.3. STATISTICAL ANALYSIS**

#### **4.3.1. Sample size calculation**

The Short Health Scale for Haemorrhoidal Disease (SHSHD), the primary outcome of this clinical investigation, was used as the basis for the calculation of the required sample size. In a study published by Renato Pietroletti et al. (2022) (7), the researchers assessed the performance of a rectal ointment based on Zn-L-carnosine in the

treatment of haemorrhoidal disease by using the SHSHD following 4 weeks of treatment with the medical device.

Their results showed an SHSHD mean  $\pm$  SD score of  $7.90 \pm 4.17$  before treatment and  $4.05 \pm 0.22$  after 4 weeks of treatment with Proctilor® rectal ointment.

Lacking the results of a similar emulsion (PROCTOeze® PLUS) we assumed a mean  $\pm$  SD SHSHD score of  $6.20 \pm 0.25$  after 4 weeks of treatment for the haemorrhoidal disease, resulting in a moderate effect size of around 0.42.

By employing a one-tailed Wilcoxon signed-rank test for matched pairs at a significant level of 2.5 % and a power of 80 % we derived a sample size of 50 evaluable patients to prove PROCTOeze® PLUS performance.

Considering a possible screen failure rate of 10% we require 55 enrollable patients.

In addition, 5 patients should account for a possible 10% moderate drop-out rate, so 60 patients should be screened for enrolment in the clinical investigation.

The software used in the calculation was G\*Power v3.1.9.7 (8).

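### The primary and secondary scales are defined at day 30, but the schedule collects them after baseline only at day 14 ± 2, and the report never gives the day of Visit 2

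*Combined protocol and SAP*

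**What the plan says.** **Outcome definitions.** Protocol Section 3.5.1 says of SHS_HD: "The questionnaire will be administered by the Investigator to each patient during the study visit, at baseline and on day 30, in PAPI mode". The Synopsis says: "The questionnaire will be completed by the patient at baseline and day 30, at the end of the treatment with the MD". For HSS, Section 3.5.1 says that it "will be completed by Investigator at baseline and day 30, at the end of the treatment with the MD". HDSS is to be administered "at baseline and on day 30, at the end of the treatment with the MD". The endpoint rows of the report's own Summary (Section 3) also give baseline and day 30 for all three scales.

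**Question and sample size.** Section 2.2 asks: "will the administration for 4 weeks of the IMD" improve symptoms? Section 4.3.1 assumes an SHS_HD score "after 4 weeks of treatment for the haemorrhoidal disease, resulting in a moderate effect size of around 0.42".

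**Schedule.** The Synopsis procedures head the second visit "Visit 2 End of Study visit (day 14", with a window of 2 days either way. Section 3.7.2.1 agrees: "The following visit (V2) will be scheduled 14" ± 2 days after Visit 1. Both schedule tables (Synopsis and Section 3.7.2) tick the three scales at Visits 1 and 2 only, and device and diary are collected at Visit 2. The day 30 ± 1 contact is a phone call. Section 3.7.2.1 lists only safety for it. The schedule tables add concomitant medication and compliance, and the Synopsis adds adherence and diary upkeep. None lists a scale.

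**Report.** Section 9 compares Visit 1 with Visit 2. It calls Visit 2 the end of treatment in the SHSHD text and the end of the study in the text to Figure 2. It gives no Visit 2 date or day.

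**The concern.** The time point is part of the definition of an endpoint. Here the outcome sections give one and the schedule gives another, and no passage reconciles them. A site cannot satisfy both, because the only day-30 contact has no questionnaire and no examination.

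The report carries the problem into its results. The Summary defines the endpoints at day 30 and then reports end-of-treatment scores. A reader will naturally take the SHS_HD fall from 14.04 to 7.80 as the answer to the 4-week question. If Visit 2 was held as scheduled, it is a two-week change, and the outcome as defined was not measured at any scheduled visit. Treatment duration is unclear for the same reason: the documents support both 14 and 30 days.

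**Working it through.** **1. What the protocol requires and what it schedules**

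| Scale | Defined at | Scheduled after baseline | Scheduled at the day-30 call |
|---|---|---|---|
| SHS_HD (primary) | day 30 | Visit 2, day 14 ± 2 | no |
| HSS (investigator) | day 30 | Visit 2, day 14 ± 2 | no |
| HDSS | day 30 | Visit 2, day 14 ± 2 | no |

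All three scales are affected, in both copies of the schedule.

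**2. Size of the gap, if the schedule was followed**

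- Nominal: 30 − 14 = 16 days.
- Smallest, with both windows: (30 − 1) − (14 + 2) = 29 − 16 = 13 days.
- Largest: (30 + 1) − (14 − 2) = 31 − 12 = 19 days.
- Share of the stated 30 days elapsed at the nominal visit: 14/30 = 47%.

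**3. What the reported exposure covers**

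The 14 daily means in Table 4 sum to 1.88 + 2.52 + 2.60 + 2.60 + 2.44 + 2.58 + 2.58 + 2.60 + 2.50 + 2.52 + 2.66 + 2.42 + 2.32 + 2.22 = 34.44. This is exactly the reported mean total, so the reported use covers days 1 to 14 and nothing later. If treatment ran to day 30, 30 − 14 = 16 days have no reported exposure.

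**4. Evidence on when treatment ended**

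| Points to 14 days | Points to 30 days |
|---|---|
| Device returned at Visit 2 (Section 3.7.2.1) | Study duration of 30 days per patient (Synopsis) |
| Diary instructions for 14 days (report Section 5) | Inclusion criterion of 30 days' self-administration (Section 3.3.1) |
| Section 9 diary text treats the study as lasting 14 days | Adherence and compliance items at the day-30 call (Synopsis, both schedules) |
| Table 4.1 stops at Day 14, read as the last days of the trial | Last patient in 17 December 2024, end of treatment (last patient out) 16 January 2025: 14 days to 31 December + 16 = 30 days |

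Nothing in the right-hand column dates Visit 2. The 30-day interval fits a last contact at day 30, which could be the phone call. The left-hand column makes a Visit 2 near day 14 probable, but it does not date the visit either.

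**5. Whether a day-30 score is reported**

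Tables 5 to 7 contain Visit 1, Visit 2 and their difference only. The CRF page for the day-30 call has tick boxes for the three scales, but no Visit 3 score is reported.

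**The case against.** The best defence is that Visit 2 may in practice have been held near day 30. The Summary states day 30 for the endpoints, and its only dated end of treatment falls 30 days after the last patient entered. That stands as a possibility. It would not clear the report: the visit would then have departed from the day-14 schedule, and exposure would be reported for the first 14 days only.

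A second defence is that sites which followed the schedule complied with one half of a contradictory protocol, so the fault is in the drafting and not in conduct. That is fair. It also stands that the Discussion and Conclusions make no explicit 4-week claim; the day-30 reading comes from the Summary's endpoint definitions.

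A reader might infer more than the documents support:

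- *That the day-30 endpoint was certainly never collected.* Actual Visit 2 dates are not given, and the CRF call page has boxes for the scales. These boxes repeat the Visit 2 list, including a physical examination that cannot be done by phone, and no schedule supports them. Non-collection is probable, not proven.
- *That the statistical methods claim compliance on timing.* The reference to the protocol in Section 9 most naturally concerns the choice of the Wilcoxon signed-rank test, not the day of assessment.
- *That the reported significance is wrong.* Nothing here shows an error in a p-value, mean or confidence interval.

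**Conclusion.** The protocol is internally inconsistent and wrong as written. SHS_HD, HSS and HDSS are defined at day 30 for a 4-week question, while the schedule can deliver them only at day 14 ± 2. This needs no assumption; it follows from the outcome sections and the schedules.

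The consequence for the results is conditional. If Visit 2 was held as scheduled, the reported changes precede the stated time point by 16 days (13 to 19), and they describe about two weeks of use, not four. That is the more likely reading, but the documents do not establish it. Whichever day Visit 2 fell on, the report needs correcting, because it states day 30 for the endpoints, analyses a visit scheduled at day 14, and does not say when that visit took place. The numerical results may stand; the time to which they refer is unknown.

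**What to change.** 1. Take the actual Visit 2 date for each patient from the CRF, establish when treatment stopped, and report both. The CRF pages shown have no field for the last application, so the stop may have to come from the device-collection boxes, the dated diary entries or source notes.
2. If Visit 2 was at about day 14: label every Visit 2 result day 14 ± 2; state that the day-30 endpoint was not collected at a scheduled visit; correct the day-30 endpoint wording in the Summary; record the mismatch in the study report, as protocol Section 5 requires for deviations; and do not present the result as the answer to the 4-week question.
3. If Visit 2 was near day 30: keep the day-30 label, report the departure from the day-14 schedule, and state that diary exposure covers only the first 14 days.
4. If the days are mixed: report their median and range.
5. Report any Visit 3 scores separately.

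The cost is a date check in 50 existing CRFs, an entry in the study report and corrected labels. No new patients or visits are needed. Follow-up is over, so a day-30 score that was not taken cannot be recovered.
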